7.0 CORRELATIVE ANALYSIS / SPECIAL STUDIES

7.1 Overview

Peripheral blood will be obtained for mRNA, miRNA, and flow cytometry analysis. While specific details of the processing, extraction, and analysis are included in this protocol, these details may change with innovations in laboratory techniques and hence are considered general guidelines only.

7.2 p16 Aging Biomarker: Identifying candidacy for treatment or transplant is generally subjective and is dependent on age, performance status, and comorbidities. The clinical need for objective quantitative measures of physiologic fitness remains unmet. As such, *p16*, a marker of cellular senescence, represents an attractive proxy for physiologic age and may be an additional tool in the clinical evaluation. Many investigations are focusing on biomarkers of age to weigh treatment options and gauge toxicity.⁵⁶ We aim to capture physiologic fitness and with use of *p16* expression in peripheral blood T-lymphocytes (PBTL). The molecular biomarker, *p16^{INK4a} (p16)* is an established marker of systemic cellular senescence associated with physiologic aging. *p16* expression increases ~16-fold over an individual's lifetime and can be readily measured in PBTL.⁵⁷

7.3 Correlative Analysis Procedures: Patients enrolled have peripheral blood collected for p16 analysis serially at three time points 1) pre-OEP 2) post-OEP and 3) 6 months. Peripheral blood will be obtained in EDTA coated tubes (10 ml) where CD3+ T-cells will be isolated using RosetteSep Reagents. RNA will be extracted using RNeasy Plus Mini Kit (Qiagen), and analyzed using reverse-transcription real-time quantitative PCR for p16, ARF, and standard housekeeping genes. p16 mRNA expression will be compared to an age-matched control dataset. The source of this dataset is a primary analysis study previously conducted by the PI, [name] (IRB protocol number 2014C0008). The only information retrieved from this control dataset will be age; no protected health information will be collected. The full dataset has been de-identified and the study team does not have access to identifiable information about this population.

7.4 Feasibility Preliminary Data: Recently, investigators have evaluated the impact of lifestyle on PBTL *p16* expression in healthy volunteers.⁵⁸ The authors reported that modifiable factors such as exercise, smoking, and body mass have an age-independent impact on *p16* expression where physical exercise duration showed an inverse association with the level of *p16* T-cell mRNA expression ($r^2=0.1922$, p<0.0001). This suggests that exercise may

exert protective effects in age-dependent accumulation of senescent cells. External factors such as chemotherapy also impact p16 expression. In preliminary data, we identified that BMT also significantly increases the expression of T-cell p16 mRNA expression in patients with multiple myeloma pre- and post-transplant (90 day). As such, we aim to explore if exercise alters p16 expression.

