3.2 Patient Selection Inclusion Criteria

- Patients with hematologic malignancy receiving care (chemotherapy, immunotherapy, targeted agents, bone marrow transplant, or other) for their hematologic malignancy at the Ohio State University.
- Age ≥ 60 years
- Impairments in physical function, as defined by a score ≤ 9 on the SPPB pre-screen
- Medical clearance from an oncologist or primary care physician stating the participant is able to participate in an unsupervised, moderate-intensity physical activity program
- Ability to understand and the willingness to sign a written informed consent document

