4.0 STUDY DESIGN

4.1 Overview

The PT will assess each patient for individualized physical therapy needs. The PT will design a PT program based upon the individual needs (e.g. weekly, bi-weekly etc). Patients will be instructed on the OEP. The OEP is a combination of physical therapist prescribed exercise and home based exercise recognized to improve balance and functional decline (**Table 1**).³³ The structured OEP focuses on strengthening, balance retraining, and walking. OEP requires minimal training and can be provided by any physical therapist. OEP home-based exercise

requires patient engagement and takes approximately 30 minutes, three times weekly, with walking twice weekly. Participants will record exercise, walking and falls in a weekly diary. The OEP physical therapy portion involves 8 visits over 4 months. All physical therapists engaged in the protocol are OEP certified. Patients will be assessed on their progress with the OEP at their twice monthly appointments. Following these appointments, patients who go on to bone marrow transplant will receive inpatient PT consults a minimum of twice weekly. During these visits, evaluation of strength, balance and walking will be assessed. Before discharge, home based exercises will be reviewed and encouraged. Documentation of physical therapy sessions will be noted and include the level of participation or lack thereof (patient in testing, unwell, declined participation). After the initial 8 physical therapy appointments, patients who will not have a bone marrow transplant will continue with their home-based exercises.

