6.3 Correlative Analysis

Presence of deleterious genes and p16 pre-OEP and post-OEP will be correlated with clinical factors (age, performance status, adherence to OEP), GA profiles, SPPB scores.

Serum studies evaluating mRNA will be characterized and analyzed in relation to functional assessment outcomes as well as clinical outcomes of interest. microRNA measures will be assessed in relation to cytokine measures using graphical analyses and measures of correlation. FDR corrections will be utilized to correct for the simultaneous comparisons of the multiple markers.

Quantified p16 expression pre and post OEP will be described, and independently analyzed in relationship to functional assessment outcomes such as GA scales, SPPB Scores as well as

clinical outcomes of interest (age). In addition, p16 expression will be evaluated in relation to clinical outcomes, such as tolerance of OEP, adherence of OEP, length of hospitalization and readmissions in a descriptive manner. Generalized linear models will be used similar to those described above to assess the impact of p16 expression on GA scores depending on data completeness. Spearman rank correlation coefficients will be used in relation to continuous measures (e.g. age), two-sample tests (Wilcoxon rank sum tests) will be used for comparing p16 expression between two groups (e.g. incidence of del17), and Kruskal-Wallis tests will be used to compare p16 expression between more than two groups. Descriptive statistics and graphical analyses will be used to evaluate p16 expression within each of the groups to better understand potential trends of interest.

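### T-cell p16 measured after an allogeneic transplant is not a reading of the patient's own physiologic age, and sections 6.3 and 7.3 have no rule for such samples

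*Combined protocol and SAP*

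**What the plan says.** **Who is enrolled.** Section 3.2 takes "Patients with hematologic malignancy receiving care (chemotherapy, immunotherapy, targeted agents, bone marrow transplant, or other) for their hematologic malignancy". It does not separate autologous from allogeneic transplant, and section 3.3 excludes neither.

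**Transplant on study.** Section 4.1 foresees it: "Following these appointments, patients who go on to bone marrow transplant will receive inpatient PT consults a minimum of twice weekly". Table 1 in section 4.5.5 has outpatient therapy running up to transplant or to four months, followed by inpatient sessions during a transplant admission.

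**What is measured.** Section 7.3 isolates CD3+ T-cells from blood at three times: "Patients enrolled have peripheral blood collected for p16 analysis serially at three time points 1) pre-OEP 2) post-OEP and 3) 6 months". No condition is attached for transplant.

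**How it is read.** According to section 7.2, p16 "represents an attractive proxy for physiologic age and may be an additional tool in the clinical evaluation". Section 7.3 adds that "p16 mRNA expression will be compared to an age-matched control dataset".

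**How it is analysed.** Section 6.3: "Quantified p16 expression pre and post OEP will be described, and independently analyzed in relationship to functional assessment outcomes". It also relates p16 to age, performance status, OEP adherence, length of hospitalization and readmissions. It names Spearman correlations, rank-sum and Kruskal-Wallis tests and generalized linear models. It has no exclusion, stratification or sensitivity analysis for samples taken after a transplant.

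**What is known about transplant.** Section 7.4 reports preliminary data in which T-cell p16 rose from before transplant to day 90 in myeloma patients. The type of transplant is not given, and no handling rule follows.

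**The concern.** The plan treats each p16 value as belonging to the person whose SPPB, geriatric assessment, age and adherence stand beside it. After an allogeneic transplant that link is broken to a varying degree, because some or all of the T-cells come from the donor. This is general biology; the documents do not discuss it.

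Three planned uses are affected:

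- **Correlations** with age, SPPB, GA and adherence would pair one person's biomarker with another person's function.
- **The age-matched comparison** would match controls to the patient's age, although the cells have the donor's age.
- **The before-after description** would contain a change of person as well as any change within the patient.

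This differs from the familiar problem that treatment raises p16 in the patient's own cells. Adjusting for or stratifying by treatment can address confounding. It cannot turn a donor's value into the patient's.

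**Working it through.** **1. Planned figure.** The plan gives no power or precision figure for p16. Its only power statement (section 6.2: 30 patients, effect size 0.55, signed-rank test, SPPB as the example) reproduces at 0.81 against the stated minimum of 80%, with two-sided alpha 0.05 assumed. It does not bear on this point.

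**2. Which draws are exposed.**

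- *6-month draw.* Visit 3 is six months after visit 1 or the first therapy appointment (section 3.6). Outpatient therapy ends by four months, so a patient transplanted at its end has about 6 - 4 = 2 months to the last draw. This draw is the most exposed. Section 7.3 collects it for p16 analysis, although 6.3 names only pre- and post-OEP p16.
- *Post-OEP draw.* Visit 2 is at OEP completion, so it usually precedes transplant. It can follow transplant because the visit window is 30 days either way in Table 2 and 45 days in Table 3, with blood taken within 14 days of the visit.
- *All draws.* A patient enrolled after an earlier allogeneic transplant gives donor-derived cells from baseline on. Nothing in 3.2 or 3.3 rules this out.

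**3. Possible size of a donor-age offset (illustration only).**

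Input from section 7.2: p16 "expression increases ~16-fold over an individual's lifetime and can be readily measured in PBTL". Assumptions, none from the documents: the rise is log-linear over 60 to 80 years, and the cells carry the donor's resting level.

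- Lifetime rise: log2(16) = 4 log2 units.
- Per year: 4/80 = 0.050 to 4/60 = 0.067.
- Offset = -(rise per year) x (patient age - donor age).

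| Donor younger by (assumed) | Offset, log2 units | p16 relative to patient |
|---|---|---|
| 0 years | 0 | 1.00 |
| 10 years | -0.50 to -0.67 | 0.71 to 0.63 |
| 20 years | -1.00 to -1.33 | 0.50 to 0.40 |
| 30 years | -1.50 to -2.00 | 0.35 to 0.25 |

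These are values for fully donor-derived cells. If half the cells are the donor's and both halves contribute equally, the 30-year offset shrinks to log2(0.5 + 0.5 x 0.354) = -0.56, up to log2(0.5 + 0.5 x 0.25) = -0.68.

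**4. Effect on a cohort mean.** Mean shift = share of affected samples x offset. With a 30-year gap and fully donor-derived cells, an assumed 5% share gives -0.075 to -0.10 log2 units, 10% gives -0.15 to -0.20, and 20% gives -0.30 to -0.40.

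**5. Direction.** Net change in an affected sample = donor offset + transplant-related change. Section 7.4 reports a rise after transplant but gives no size. A rise of 2^1.5 = 2.8-fold to 2^2 = 4-fold would cancel the 30-year offset; a larger one would reverse it. The net sign therefore cannot be fixed from the documents.

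**The case against.** The strongest reply is that the problem may hardly touch the stated analysis. Section 6.3 names p16 before and after the OEP, and the schedule usually places the post-OEP sample before transplant. The most exposed sample, at six months, appears only in 7.3. Allogeneic enrolment is itself an inference: the word occurs only in the title of a cited study, and the AML/ALL laboratory entries under Table 3 show disease type, not transplant type. p16 is exploratory throughout.

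All of this stands and limits the point. It does not remove it. Section 7.3 collects the 6-month draw expressly for p16 analysis, the windows leave a route for post-OEP samples, and the eligibility text admits any transplant, including an earlier one.

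Two stronger readings are tempting. A reader might infer that younger donor cells would make exercise appear to lower p16. The documents do not support this: they give no donor ages, and their only evidence on transplant is a rise. A reader might also convert the offset into a false-positive rate for a paired signed-rank test. That test is specified in 6.2 for GA, falls, SPPB and PROMIS. Section 6.3 says that p16 before and after the OEP will be described and names no paired test for it, so such a rate would not be the error rate of any planned p16 analysis.

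**Conclusion.** The gap is real and worth closing, as a cheap improvement to an exploratory analysis. As written, a sample drawn after an allogeneic transplant could enter the p16 correlations, the age-matched comparison and the before-after description as if it were the patient's own reading.

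The conclusion rests on two premises: that the unqualified eligibility text admits allogeneic transplant patients, and that T-cells after such a transplant are wholly or partly the donor's. It does not rest on the illustrated offset. Even with a donor of the patient's own age, where the offset is zero, the value would still not describe the patient.

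The number of affected samples, the size of the distortion and its direction are unknown. The range of 1.5 to 2.0 log2 units holds only for an assumed 30-year age gap, an assumed 60- to 80-year span, fully donor-derived cells and no transplant-related rise. The primary feasibility endpoint is unaffected.

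**What to change.** - **Sections 6.3 and 7.3:** state that p16 samples drawn after any allogeneic transplant, including one before enrolment, are excluded from all p16 analyses: the before-after description, the correlations and models, and the age-matched comparison. List these samples separately with their number and draw time. Keep the patient's samples from before the transplant.
- **Section 5.4:** add transplant type and date explicitly, including for transplants before enrolment. The present list names transplant length of stay and outcomes, but neither of these items. They might be found under treatment history, but the exclusion should not depend on that.

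The cost is a sentence in each analysis section and two data items. A few exploratory p16 samples are lost, and the before-after p16 results will then describe only patients not allografted by the time of the draw, which the report should say. No visit, blood draw or clinical procedure changes.

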3.3 Patient Selection Exclusion Criteria

- Prisoners
- Any medical condition including, but not limited to, symptomatic congestive heart failure, unstable angina pectoris, cardiac arrhythmia, or psychiatric illness that would limit compliance with study procedures.

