To obtain T cells: Whole blood collected in a purple top EDTA tube will be divided into two equal volume portions, approximately 5mL each. RosetteSep Human T Cell Enrichment Cocktail (Stem Cell Technologies # 15061) will be added to each tube at a ratio of 50uL per mL of whole blood. Tubes will be mixed by inversion and incubated for 20 minutes at room temperature. Next, samples will be diluted in an equal volume of phosphate buffered saline containing 2% fetal bovine serum (PBS/2%FBS). Diluted samples will be gently mixed and then carefully layered on top of Histopaque 1077 density medium (Sigma-Aldrich #10771) in a 50mL conical tube. The amount of density medium used will equal the original blood aliquot volume (~5mL). Tubes will then be centrifuged at 1200xg for 20 minutes at room temperature with the centrifuge brake set to 'off'. Following separation, enriched T-cells will be removed from the plasma interface using a pipette and placed into a fresh 15mL conical tube. The cells will be washed by adding PBS/2%FBS to the tubes until they are filled to the top fill line. Tubes will then be centrifuged at 400 x g for 4 minutes at room temperature with maximum brake. The resulting supernatant will be removed with a pipette and transferred to a 1.5 mL microcentrifuge tube. This sample will be centrifuged at 400 x g for 4 minutes at room temperature with maximum brake. The resulting supernatant will be carefully and completely removed using a pipette. The remaining T-cell pellet will be stored in a -80 $^{\circ}$ freezer until processing.

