Under the supervision of [name], harvested T-cell mRNA will be converted to cDNA using the Promega ImProm-II Reverse Transcription System (Promega #A3802) and random hexamer primers (Invitrogen #588875) as directed by the manufacturers. p16 levels will be measured using a Taqman-based quantitative RT-PCR methods essentially as described by Liu et al. (20). Validated Taqman-based controls for T-cell purity (CD3G, Applied Biosystems #4331182 Hs00962186), sample viability (p14ARF, Applied Biosystems #4351370 HUMP14-ARF3) and RNA quantity (YWHAZ, Applied Biosystems #4331182 Hs03044281) are included in this analysis. Data clean up: Data will be filtered to exclude relatively invariant features (IOR = 0.5) and features below the detection threshold (defined for each sample by a cutoff corresponding to approximately twice standard deviation of negative control probes plus the mean of them) in at least half of the samples. Basic analysis Using R/Bioconductor and the filtered dataset, linear models for microarray data analysis⁵⁹ (Smyth et al., 2005) will be employed with a contrast matrix for the comparisons. P values will be used to rank miRNAs and mRNA of interest, and correction for multiple comparisons will be done by the Benjamini-Hocheberg method⁶⁰ (Benjamini et al., 1995). Raw data that is above background, as well as the corresponding quantile-normalized data, will be imported into MultiExperiment Viewer⁶¹ (Saeed et al., 2006; Pichiorri et al. 2013).

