8.0 STUDY CALENDAR

Table 3. Study Visit Assessments					
	Study Visit 1: Baseline* (+/- 45 days)	Study Visit 2: POST-OEP Evaluation *(+/- 45 days)	Study Visit 3: 6 Month Follow up *(+/- 45 days)		
Signed Informed Consent	Х				
Inclusion/Exclusion Criteria	Х				
Registration additions	Х				
History and Physical	Х	Х	Х		
Weight and Height ^a	Х	Х	Х		
Adverse Events ^b	Х	Х	Х		
KPS	Х	X	Х		
Vitals	Х	Х	Х		
CBC with differential ^c	Х	Х	Х		
Serum Chemistry and LFT's ^d	Х	X	Х		
Hematologic Cancer Specific Labs ^e	Х	Х	Х		
β2 microglobulin, LDH, CRP	Х	X	Х		
Peripheral blood for biomarker analysis ^f	Х	X	Х		

a. Weight to be measured in the same fashion at each time point (with or without shoes, street clothes vs. gown, etc). Height does not need to be repeated after the screening visit.b. Adverse events (AE) and their severity will be captured according to the CTCAE v4.0 and

whether any AEs can be attributed to exercise (physical therapist administered or home based).

c. CBCs will be performed to include at least WBC, hemoglobin, platelets, and absolute neutrophil count.

d. Serum chemistry (electrolytes, BUN, creatinine) and Liver function tests to include transaminases and albumin

e. Myeloma: measure clinically relevant proteins that have previously been abnormal in that patient to include more than one of the following: a) serum immunoglobulins by nephelometry, b) serum & urine protein electrophoresis and immunofixation, c) serum free light chains; and d) 24hr urine total protein (as necessary); NHL: LDH; AML/ALL: % circulating blasts

f. Blood samples (30 mL of blood) will be cryopreserved for correlative analyses (RNA studies, flow cytometry etc.)

* Survey participant data will be captured as part of routine care

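### Blood T-cell p16 is read as physiologic age with no rule for T-lineage malignancy, so a few readings in the exploratory p16 analyses could reflect tumour

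*Combined protocol and SAP*

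**What the plan says.** - **Who is eligible.** Section 3.2 takes "Patients with hematologic malignancy receiving care (chemotherapy, immunotherapy, targeted agents, bone marrow transplant, or other") without restriction by lineage. Section 3.3 excludes prisoners and patients with "Any medical condition including, but not limited to, symptomatic congestive heart failure, unstable angina pectoris, cardiac arrhythmia, or psychiatric illness" that would limit compliance. Neither mentions lineage.
- **Which diseases the calendar provides for.** Footnote e of Table 3 (section 8.0) sets laboratory tests by disease. After myeloma it lists "NHL: LDH; AML/ALL: % circulating blasts", with no split into B- and T-lineage forms.
- **What is assayed.** Section 7.3 describes EDTA blood "where CD3+ T-cells will be isolated using RosetteSep Reagents". Section 7.6 gives the bench step: "RosetteSep Human T Cell Enrichment Cocktail (Stem Cell Technologies # 15061) will be added to each tube". This is bulk enrichment, and no step separates clonal from normal T-cells.
- **How the assay is controlled.** Section 7.8 lists "Validated Taqman-based controls for T-cell purity (CD3G"), p14ARF for sample viability and YWHAZ for RNA quantity.
- **How the result is used.** Section 7.2 treats T-cell p16 as an indicator of physiologic age. Section 6.3 relates it to age, GA scales, SPPB, adherence and hospital outcomes by Spearman correlation, rank-sum and Kruskal-Wallis tests, and generalized linear models. Section 7.3 adds a comparison with an age-matched control dataset. The only named two-group example is del17. No exclusion, stratum or sensitivity analysis by lineage appears.

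**The concern.** In most eligible diseases the CD3-positive cells are not the tumour, and p16 in them can carry the meaning the plan gives it. In a T-lineage leukaemia or lymphoma with circulating CD3-positive disease, the enriched fraction may be partly or largely tumour. Section 2.3 describes p16 as a tumour suppressor that blocks the cell cycle, so its level in a malignant clone cannot be assumed to track age or fitness. CD3G confirms that the cells are T-cells. It would not flag malignant T-cells that express CD3.

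At stake are the p16 associations with SPPB, GA and age, and the comparison with controls. If treatment clears circulating disease between visits, the pre/post description is exposed as well. Section 2.1 presents p16 against physical performance as a novel aim, so a handful of uninterpretable values in a small sample deserves a rule set in advance.

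**Working it through.** **Text check.** Four places could have dealt with T-lineage disease:

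1. Eligibility (3.2, 3.3): no lineage criterion.
2. Isolation (7.3, 7.6): enrichment of all T-cells, with no clonality step.
3. Assay controls (7.8): T-cell identity, viability and RNA quantity. None addresses malignancy.
4. Analysis (6.3): no lineage rule. Flow cytometry (7.1, Table 3 footnote f) and T-cell subpopulations (2.3) are mentioned, but neither is tied to the p16 sample as a check.

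**Scale.** The plan states no figure to reproduce: it gives no power for p16, no share of T-lineage patients, and no tumour-versus-normal difference. Everything below rests on assumptions.

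*Chance of at least one T-lineage patient*, 1 - (1 - s)^n, at an assumed share s = 2%:
- n = 100 (the maximum in 3.6): 1 - 0.98^100 = 87%.
- n = 30: 1 - 0.98^30 = 45%.

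This counts diagnoses. The number with circulating CD3-positive disease would be the same or smaller.

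*Inflation of the p16 SD.* Let a fraction f of patients be shifted by d log2 units, with a between-patient SD of 1 log2 unit (assumed). The multiplier is sqrt(1 + f(1 - f)d²). The larger shift, d = 4, borrows the roughly 16-fold lifetime rise in 7.2 (log2 16 = 4). That is an ageing range, used here only as an upper illustration. The n = 30 comes from the SPPB power example in 6.2.

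| Affected of 30 | f(1 - f) | d = 2 | d = 4 |
|---|---|---|---|
| 1 | 0.0322 | sqrt(1.129) = 1.06 | sqrt(1.516) = 1.23 |
| 2 | 0.0622 | sqrt(1.249) = 1.12 | sqrt(1.996) = 1.41 |
| 3 | 0.0900 | sqrt(1.360) = 1.17 | sqrt(2.440) = 1.56 |

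*Power to detect a true correlation of 0.4*, by simulation (n = 30, two-sided 5%, affected values shifted by d). Ranges show the spread over repeated runs, and any single figure is good to a point or two.

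| Affected of 30 | Spearman, d = 2 | Spearman, d = 4 | Linear, d = 2 | Linear, d = 4 |
|---|---|---|---|---|
| 0 | 55% | 55% | 61% | 61% |
| 1 | 51-52% | 48% | 55% | 41-42% |
| 2 | 47-49% | 43-44% | 50-51% | 32% |
| 3 | 42-45% | 40% | 44-47% | 27-28% |

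Reversing the sign of the shift leaves these results essentially unchanged. At n = 100 with 3 affected and d = 4, Spearman power is 96% against 98%. Holding the share at 10% instead (10 of 100, d = 4), the same simulation gives about 89%. The slight loss at n = 100 therefore holds for a few affected patients, not for a 10% share.

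*Pre/post change.* If the tumour contribution at visit v is c(v), the observed change is the true change plus c(2) - c(1). A constant contribution cancels. Bias arises only when circulating tumour burden changes between visits.

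**The case against.** Several objections have force.

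- **Pooling is not mandated.** A reader might infer that 6.3 analyses all patients as one group. It does not say so. The entire-cohort wording is in 6.2 and covers the GA, falls, SPPB and PROMIS. Section 6.3 allows group comparisons and graphs within groups, where an extreme cluster might show. What remains is that lineage is never named, so any omission would be decided after seeing the values.
- **T-lineage enrolment is not shown.** A reader might take "AML/ALL: % circulating blasts" in Table 3 as evidence that such patients are expected. It is a list of laboratory tests, and no T-cell malignancy is named anywhere. That NHL and ALL include T-lineage forms, and that some of these circulate and express CD3, is general knowledge. The documents support only that such patients may enter.
- **The size is assumed.** The share, the shift, its direction and n = 30 are all unsupported for p16, and the calculation treats every counted patient as affected. The steepest losses are the linear ones, while 6.3 names Spearman for continuous measures. Generalized linear models of GA scores on p16 are also planned, depending on data completeness, so the linear column is relevant but not representative.
- **Laboratory flexibility.** Section 7.1 calls the processing details general guidelines. That covers technique and does not settle whose values enter an analysis.
- **Exploratory status.** The primary endpoint is feasibility, p16 has no decision rule, and diagnosis is recorded (5.4), so a sensitivity analysis remains possible later. This limits the severity but leaves the case for prespecification intact.

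**Conclusion.** The point holds in limited form. As written, the plan would allow tumour-derived readings to enter analyses that interpret p16 as physiologic age, because eligibility is open to all lineages and no assay control or analysis rule sets T-lineage disease aside. It applies only to patients with circulating CD3-positive malignant T-cells, and it touches only the exploratory associations, the control comparison, and pre/post change where tumour burden changes.

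The size cannot be derived from the documents. Under the assumptions above, 1 to 3 affected patients of 30 inflate the SD 1.06-1.17 fold (2 units) or 1.23-1.56 fold (4 units). Spearman power falls from about 55% to 52-42% or 48-40%, with little loss when 3 of 100 are affected.

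A reader might go further and conclude that the p16 results as a whole are invalid, or that every pre/post comparison is biased. The documents support neither: they establish no affected patient, and a constant offset cancels within a patient. This is an optional improvement that bears on no primary conclusion.

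**What to change.** In 6.3 and 7.3, prespecify that:

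- the main T-cell p16 analyses omit patients with a T-lineage malignancy, identified from the diagnosis already collected under 5.4;
- the p16 values of those patients are listed separately;
- the all-patient analysis is reported as a sensitivity check.

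Enrolment and sampling do not change. The cost is a few lines of analysis text, best written before p16 results are seen so that the handling of outliers is not a post hoc choice. The downside is a small loss of exploratory sample. A rule by diagnosis also drops some T-lineage patients without circulating disease, whose samples would be valid, and the all-patient sensitivity analysis keeps their data in view.
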